3.5 Accountability Procedures

The investigator (or designee) is responsible for maintaining accurate inventory records of the investigational product.

Refer to Section [5.1.5](#) for Investigational Product Accountability.

3.6 Maintenance of Study Intervention Randomization

As this study will be open label, there are no procedures for breaking randomization codes. Refer to Section [3.3.2](#) for Treatment Assignment/Randomization.

3.7 Data Directly Recorded on the Case Report Form

There are no planned data to be recorded directly on the eCRF that would be considered source data.

Refer to Section [9.3](#).

3.8 End of Study

End of study is defined as the last subject's last visit (LSLV). An individual participant is considered to have completed the study after completing the last study visit, Day 57 and all AEs have been followed to resolution or diagnosis. The study could be terminated early if stopping rules are triggered and the SMC or Emergent determines the study should be stopped.

3.8.1 Terminating the Study

The Sponsor reserves the right to stop or terminate the study at any time for clinical or administrative reasons.

Any decision to voluntarily suspend or terminate a clinical study will be carefully reviewed and fully justified. The Sponsor will notify the applicable regulatory authority country regulatory agency of any suspension or termination, along with justification for terminating the study.

The PI must notify the IRB/IEC/REB in writing of the study's completion or early termination. The Sponsor must receive a copy of the notification letter from the IRB/IEC/REB indicating receipt of the completion or early termination letter.

3.8.2 Terminating the Study at an Individual Investigational Site

An investigational site may be terminated from the study at the discretion of the Sponsor or IRB/IEC/REB for reasons such as non-compliance, lack of recruitment, fraud or blacklisting by the regulatory authorities, etc.

Anti-SARS-CoV-2 Immunoglobulin Intravenous (Human) (NP-028), abbreviated as COVID-HIG
EBS-CVH-006, Version 3.0, 18 Feb 2022

The Sponsor may decide to replace a terminated investigational site.

4 SELECTION AND WITHDRAWAL OF SUBJECTS

4.1 Subject Inclusion Criteria

All participants must meet all the following inclusion criteria in order to be enrolled into the study:

1. Able and willing to provide written informed consent (voluntarily signed by the participant) prior to performing study procedures.
2. Females and males 18–59 years of age.
3. Have a BMI less than or equal to 35.0 kg/m².
4. Healthy, based on medical history (no chronic disease, no chronic therapy, no ongoing acute condition within four weeks prior to dosing), normal physical examination (no clinically significant findings in the opinion of the investigator), and screening laboratory assessments (no clinically significant findings in the opinion of the investigator).
5. No clinical symptoms suspicious for COVID-19 infection, as well as SARS-CoV-2 IgM antibody negative and no laboratory evidence of current SARS-CoV-2 infection (i.e., RT-PCR negative for SARS-CoV-2) at Screening.
6. Females must not be pregnant, or trying to become pregnant as demonstrated by either of the following A or B:
 - A. Not of childbearing potential: surgically sterile (at least six weeks post bilateral salpingectomy, bilateral oophorectomy, or hysterectomy); or post-menopausal (history of \geq 12 consecutive months without menses prior to randomization in the absence of other pathologic or physiologic causes and confirmed by follicle FSH level \geq 40 mIU/mL); OR
 - B. Women of childbearing potential who are not planning to be pregnant during the study period and who meet all of criteria i–iii:
 - i. Negative serum pregnancy test at the Screening Visit.
 - ii. Negative urine pregnancy test on Day 1 (a positive test will result in discontinuation from intervention).
 - iii. Using one of the following highly effective methods of contraception during the study:
 - Combined estrogen and progestogen, or progestogen-only hormonal contraception associated with inhibition of ovulation (e.g., implants, pills, patches) initiated \geq 30 days prior to Study Day 1.
 - Intrauterine device or hormone releasing IUS inserted \geq 30 days prior to Study Day 1.

Anti-SARS-CoV-2 Immunoglobulin Intravenous (Human) (NP-028), abbreviated as COVID-HIG
EBS-CVH-006, Version 3.0, 18 Feb 2022

7. Participant understands and agrees to comply with planned study procedures.

4.2 Subject Exclusion Criteria

Participants who meet any of the following criteria cannot be enrolled:

1. Use of any investigational product within 30 days or SARS-CoV-2 monoclonal antibodies and COVID-19 convalescent plasma within 90 days prior to Screening or anticipated receipt during the study follow-up period, or participant plans to participate in another clinical study during the study period.
2. Receipt of 1 or 2 doses COVID-19 vaccine within 60 days prior to screening or anticipated receipt during the study follow-up period.
3. SARS-CoV-2 IgG antibody levels >80 AU/mL as determined by the Diasorin LIAISON SARS-CoV-2 S1/S2 IgG antibody assay.
4. Screening clinical laboratory test result greater than the laboratory's ULN for ALT, AST, random glucose, total and/or direct bilirubin, BUN, or creatinine. Other serum chemistry parameters that are not within the reference range will not be considered exclusionary unless deemed clinically significant by the PI.
5. Positive laboratory evidence of current infection with HIV, HCV, or HBV. Note: Positive anti-HCV antibody result along with a negative HCV PCR would NOT be exclusionary.
6. History of allergy or hypersensitivity to blood or plasma products or to COVID-HIG excipients (proline, PS80).
7. History of allergy to latex or rubber.
8. History of hemolytic anemia.
9. History of IgA deficiency.
10. Receipt of any blood product within the past 12 months.
11. Plasma donation within 7 days or blood loss/donation (>450 mL) within 56 days of dosing.
12. History of known congenital or acquired immunodeficiency or receipt of immunosuppressive therapy (e.g., prednisone or equivalent for more than two consecutive weeks within the past three months).
13. History of thrombosis or hypercoagulable state with increased risk of thrombosis.
14. Receipt of a live vaccine within 30 days prior to screening or anticipated receipt of a live vaccine during the study period.
15. Currently pregnant, breastfeeding, or planning to become pregnant during the study.
16. History of, or suspected substance abuse problem (including alcohol).
17. Any planned elective surgery or procedure during the follow-up period that impacts study compliance.

Anti-SARS-CoV-2 Immunoglobulin Intravenous (Human) (NP-028), abbreviated as COVID-HIG
EBS-CVH-006, Version 3.0, 18 Feb 2022

18. Other condition which may place participant at increased risk due to participation in the study or may impact study compliance as determined by the investigator.
19. An opinion of the investigator (or designee) that it would not be in the best interest of the individual to participate in the study.

4.3 Subject Withdrawal Criteria

4.3.1 Withdrawal of Consent

All participants are free to withdraw from participation in this study at any time, for any reason. The PI will request (but cannot require) such participants to provide the reason(s) for withdrawal of consent.

Outreach will be made to ensure that participants who withdraw from the study during the active treatment or follow-up period will complete all safety and available assessments for the Early Withdrawal visit as outlined in this protocol. The PI should inform the participant that these assessments are for their own well-being and, if possible, for study purposes. Additional information regarding ongoing adverse events may be provided as a follow-up report.

The participant must first agree to the collection of early withdrawal and safety assessments prior to the assessments, and this agreement must be documented in the source documents.

Safety follow-up for adverse events should occur for all participants.

4.3.2 Discontinuation of Intervention

If applicable based on randomized route of administration, the injection(s) can be stopped if Grade 2 or higher or serious AE (anaphylaxis or hypersensitivity reaction) are observed. All participants should still be followed-up for the duration of the study for safety. Refer to Section [5.1.4](#) for further information related to AEs and administration of IP.

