Potential for injection-related local (e.g., pain, redness, tenderness or swelling) and systemic (back or abdominal pain, nausea and vomiting, fever, headache, myalgia, chills, rash, or fatigue) reactions.	These are common adverse reactions seen with other human hyperimmune products (VARIZIG, HepaGam B, ANTHRASIL, WinRho SDF, CNJ-016-VIGIV, BIVIGAM®, GAMMAPLEX®, Privigen®, GAMUNEX®-C, Hizentra®) (30, 31, 32, 33, 34, 35, 36, 37, 38, 39).	The IM dose will be administered to the thigh muscle and will be split between both thigh muscles to mitigate discomfort. All study participants will stay overnight in the inpatient unit for close observation for approximately 24 hours post injection. Injection stopping rules and study stopping rules are provided (Pharmacy Manual and Sections 3.4).
Potential for hypersensitivity reactions within six hours after the injection.	Hypersensitivity reactions are rare. Severe immediate hypersensitivity reactions to plasma-derived products occur in individuals with IgA deficiency or hypersensitivity to human globulin.	Participants will be monitored overnight after injection in a setting with appropriate equipment, medication and personnel trained in the management of hypersensitivity, anaphylaxis, and shock. Participants at risk of hypersensitivity reactions are excluded from the study.
Potential for renal dysfunction/acute renal failure.	Renal dysfunction has been associated with HIG products containing sucrose as a stabilizer.	COVID-HIG does not contain sucrose. Serum blood urea nitrogen and creatinine will be monitored at Screening and at Day 2 and Day 4 post-administration.
Potential for hematologic complications such as hemolytic anemia and thrombotic complications.	Rare thrombotic events have been associated with presence of activated factor XI resulting in elevated procoagulant activity in some immunoglobulin products. High doses (>1–2 g/kg) are associated with an increased risk of hemolysis.	COVID-HIG has been tested for procoagulant activity and has met the product release specification. The COVID-HIG doses being administered are well below 1 g/kg. Hemoglobin will be monitored at Screening and at Day 2 and Day 4 post-administration. Participants with pre-existing thrombotic or procoagulant disorders are excluded from the study.

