5.1.4 Investigational Product Administration

Investigational product is to be administered only under the direct supervision of the PI or qualified investigational site personnel. An acute observation period after IP administration will occur (Section 6.5.1) where the participant will be monitored by study staff for signs of an acute adverse reaction after administration.

Participants will be monitored in-clinic closely during injection and overnight in-clinic. A detailed safety follow-up for participants will occur one day and three days post-dose (Days 2 and 4).

If AEs occur during or immediately after the injection, such as grade 1 (mild) events of flushing, headache, chills, fatigue, nausea, slight changes in pulse rate or blood pressure, slow the rate of injection until symptoms subside or until dose is completely administered (at discretion of the investigator). If the recipient experiences grade 2 (moderate) or higher AEs such as chest pain, difficulty breathing, vomiting, arthralgia, or severe headache, unresponsive to slowing or stopping the injection, halt the injection and wait until symptoms subside to determine whether to resume injection.

Depending on the route of administration, the participant may receive multiple injections of COVID-HIG to achieve the full dose in the study arm. Stop the injection if serious AEs develop (e.g., anaphylaxis, severe hypersensitivity reactions) and administer appropriate medical management. Do not complete the injection.

Anti-SARS-CoV-2 Immunoglobulin Intravenous (Human) (NP-028), abbreviated as COVID-HIG
EBS-CVH-006, Version 3.0, 18 Feb 2022

For additional details regarding administration of COVID-HIG please see the IB and Pharmacy Manual.

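### For serious adverse events, stopping an injection is optional in Protocol 4.3.2 but mandatory in 5.1.4, whose Grade 2 or higher instruction is also circular

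*Protocol*

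**What the plan says.** Protocol 4.3.2 (Discontinuation of Intervention) limits itself to cases where the randomized route makes it applicable. It then says that "the injection(s) can be stopped if Grade 2 or higher or serious AE (anaphylaxis or hypersensitivity reaction) are observed". It sets no precondition and refers to 5.1.4 "for further information related to AEs and administration of IP".

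Protocol 5.1.4 (Investigational Product Administration) gives three graded instructions:

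- Grade 1 events: "slow the rate of injection until symptoms subside or until dose is completely administered (at discretion of the investigator"). Discretion is written into this instruction.
- Grade 2 or higher: "If the recipient experiences grade 2 (moderate) or higher AEs such as chest pain, difficulty breathing, vomiting, arthralgia, or severe headache", and these are "unresponsive to slowing or stopping the injection, halt the injection and wait until symptoms subside to determine whether to resume injection".
- Serious events: "Stop the injection if serious AEs develop (e.g., anaphylaxis, severe hypersensitivity reactions) and administer appropriate medical management. Do not complete the injection".

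Table 3 in Protocol 1.3.1 says where the rules are to be found: "Injection stopping rules and study stopping rules are provided (Pharmacy Manual and Sections 3.4"). It names neither 4.3.2 nor 5.1.4. Section 3.4 contains sponsor-level holds on enrollment and dosing, triggered by counts of events across participants. It has no rule for an individual injection.

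On the analysis side, the synopsis lists a primary safety endpoint for adverse events that end or temporarily interrupt dosing. Protocol 3.2.3.1 and SAP 3.3 do not list it. SAP 6.3 defines an event causing discontinuation of treatment by the action code Drug Withdrawn. SAP 9.2.1 and 9.3.3 tabulate those events, and no SAP table covers temporary suspension.

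**The concern.** This is the participant-level safeguard for an acute reaction during dosing, and the protocol states it in two places that do not match. Site staff who read 4.3.2 may treat stopping as a judgement in a case where 5.1.4 gives an order. Staff who read 5.1.4 find an instruction for Grade 2 or higher events that cannot be applied literally, and which overlaps the instruction for serious events.

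The second stake is classification. Whether a dose was slowed, paused and resumed, or stopped for good determines whether the related event counts as a discontinuation, a suspension or neither. If the rule is unclear and only one action code feeds the tables, the synopsis endpoint cannot be reported as defined.

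**Working it through.** No arithmetic applies. The check sets trigger, condition, force and resumption side by side for each type of event.

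| Event | Protocol 4.3.2 | Protocol 5.1.4 | Same action? |
|---|---|---|---|
| Grade 2 or higher, not serious, settles on slowing | Stopping permitted | Halt instruction not triggered; no explicit instruction for an event that responds | Compatible, but not the same rule |
| Grade 2 or higher, not serious, does not settle | Stopping permitted | Halt, wait, then decide on resuming | Optional against required |
| Serious, including anaphylaxis | Stopping permitted | Stop, and do not complete | Optional against required and final |
| Serious and Grade 2 or higher | Stopping permitted | Meets both instructions: possible resumption under one, no completion under the other | 5.1.4 overlaps itself |

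**Circularity.** The halt in 5.1.4 applies to an event that has not responded to slowing or stopping.

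- If stopping was tried and failed, the instruction is to halt an injection that is already stopped.
- If stopping was tried and worked, the condition is not met, and the text does not say whether the injection may resume.
- Only the branch in which slowing alone failed gives a usable instruction.

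This defect belongs to the Grade 2 or higher instruction alone. The serious-event instruction is unconditional.

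**Discretion.** Investigator discretion is stated for Grade 1 and absent from the other two instructions. It cannot simply be read into them to bring 5.1.4 into line with the permissive wording of 4.3.2.

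**Precedence.** The cross-reference from 4.3.2 offers further information and does not say that 5.1.4 governs. Following Table 3 to Section 3.4 leads to study-level holds only. The Pharmacy Manual, which Table 3 also names, is not among the documents. It may hold a fuller rule, but that would not cure conflicting protocol text.

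**Classification.** The synopsis endpoint has two components, ending and temporarily suspending administration. SAP 6.3 provides a definition for the first only. Its separate definition of completed treatment rests on a single eCRF question about whether the injection went as planned. As described, that question does not separate a slowed dose from a paused or abandoned one.

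**The case against.** The strongest reply is that 4.3.2 is a short enabling statement and 5.1.4 is the procedure. Because 4.3.2 only permits stopping, it forbids nothing that 5.1.4 requires, and a site that follows 5.1.4 complies with both. That is correct. A reader might infer that staff face two incompatible orders, and the text does not support this. What stands is that the reverse does not hold: a site relying on 4.3.2 alone could depart from 5.1.4, and the protocol does not say which text governs.

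Other stronger readings also fall short:

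- **Scope of hypersensitivity.** A reader might infer that 4.3.2 covers every hypersensitivity reaction and 5.1.4 only severe ones. The bracket in 4.3.2 qualifies serious events, and the list in 5.1.4 is introduced as examples. Both are serious-event triggers.
- **Bias between routes.** A reader might infer that inconsistent handling would appear as a route difference in safety or PK. The same text applies to all three arms, and no mechanism for a route-specific effect is shown. PK inclusion follows the population definitions and deviation review.
- **Size in percentage points.** With 7-8 participants per arm, one participant is 1/8 = 12.5% to 1/7 = 14.3% of an arm. That is the granularity of any yes/no outcome at this sample size. It does not measure how often the two sections would lead to different actions.

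It is also fair to say that dosing is supervised by the investigator or qualified staff. Total volume is recorded under Protocol 5.1.3, with start and stop times where applicable, and SAP 9.1 tabulates volume, so an incomplete dose would be visible. A pause followed by full delivery would not show in the volume. Finally, Version 3.0 already reports truncation at 23 randomized participants, each given a single Day 1 dose, so little or no dosing may have remained for new wording to affect.

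**Conclusion.** The point holds as an internal inconsistency of lower severity. Three defects are established from the text:

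- the optional-against-mandatory mismatch for serious events;
- the circular condition for Grade 2 or higher events;
- the overlap within 5.1.4 on resumption.

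The absence of stated precedence and the Table 3 pointer to Section 3.4 leave them unresolved.

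No numerical size can be attached. The documents report no participant handled differently because of the wording, so the harm is potential. The conclusion assumes that the Pharmacy Manual does not override the protocol, and it takes no view on which clinical rule is right. If dosing is complete, as the truncation suggests, the remaining value is mainly in classifying interrupted doses for analysis and in any later reuse of the text.

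**What to change.** The sponsor's clinical team should reconcile 4.3.2 and 5.1.4 into one rule kept in one section. For each severity level and for serious events, the rule should state whether action is required or optional and whether the injection may resume. It should also say which instruction governs when an event meets more than one. Section 4.3.2 should then refer to that rule, and the Table 3 pointer should be corrected. The clinical content is for the sponsor to decide.

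For analysis, record slowed, paused-and-resumed and permanently stopped doses as separate categories on the eCRF. Add a SAP definition and table for events leading to temporary suspension alongside the existing one for Drug Withdrawn. Align the endpoint lists in the synopsis, Protocol 3.2.3.1 and SAP 3.3.

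The cost is protocol wording plus a small eCRF and SAP change. If dosing is already complete, classify any affected doses from the recorded times, volumes and source notes, and describe the classification in the study report. No new data collection from participants is needed.

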4.3.3 Subject Withdrawal Criteria

The PI may withdraw a participant from further IP administration or participation in the study, at their discretion, if medically necessary or for reasons of noncompliance. The reason for withdrawal of any participant must be clearly documented on the study source documents and the appropriate electronic Case Report Form (eCRF). The PI is encouraged to consult the Sponsor prior to the withdrawal of any participant, except in the event of a medical emergency.

The PI (and/or the Sponsor) may withdraw a participant from further IP administration or participation in the study for any of, but not limited to, the following reasons:

- Lost to Follow-up
 - Lost to follow-up determination requires documentation of at least 3 unsuccessful attempts to contact participants.
- Adverse Event

Anti-SARS-CoV-2 Immunoglobulin Intravenous (Human) (NP-028), abbreviated as COVID-HIG
EBS-CVH-006, Version 3.0, 18 Feb 2022

- Protocol Deviation
- Pregnancy
- Physician (i.e., PI) Decision
- Withdrawal by Subject
- Participant contracts COVID-19
- Participant receives prohibited COVID-19 vaccination
- Other

Safety follow-up for adverse events should occur for all participants.

Reasons for withdrawal of individual participants from the study prior to final protocol required visit and/or final safety follow-up are to be recorded on the CRF and subject source documents.

A participant who is withdrawn from the study will not be re-entered into the study for any reason.

4.3.4 Subject Replacement

Participants who are discontinued or withdraw consent prior to baseline/randomization after signing consent will be replaced. Participants withdrawn from the study or who withdraw consent after randomization will not be replaced, regardless of whether they have been dosed. The study sample size determination has included consideration for some participants to be lost to follow-up or withdraw consent.

5 STUDY INTERVENTION

5.1 Investigational Product(s)

Anti-SARS-CoV-2 Immunoglobulin Injection (Human), also referred to as COVID-HIG, is a hyperimmune product that consists of purified IgG fraction of human plasma containing antibodies (including neutralizing antibodies) to SARS CoV-2. The product is a clear to slightly opalescent and colorless or pale, yellow liquid essentially free of foreign particles. The final sterile liquid product contains 85-115 mg/mL of human plasma proteins (target 100 mg/mL), of which at least 90% is human IgG. COVID-HIG is formulated with 250 mM proline and 0.03% (w/w) PS80 and has a pH between 5.5 and 6.0 (target pH 5.8). The final product contains no preservatives.

The potency of the final product is determined by a validated immunoassay that measures concentration of binding SARS-CoV-2 antibodies (with SARS-CoV-2 trimeric S protein as the antigen) in relation to a reference standard; the final drug product is also characterized by a wild-type SARS-CoV-2 neutralization assay (refer to the most current version of the IB).

COVID-HIG will be administered as a single \approx 250,000 AU dose through an IM, SC, or IV route of administration. Based on a calculated potency of 29,282 AU/mL as assessed using a wildtype neutralization assay, this will equate to an 8.5 mL (\sim 850 mg, based on a target protein

Anti-SARS-CoV-2 Immunoglobulin Intravenous (Human) (NP-028), abbreviated as COVID-HIG
EBS-CVH-006, Version 3.0, 18 Feb 2022

concentration of 100 mg/mL) dose that may be split across several sites, depending on route of administration.

For additional information, refer to the IB and Pharmacy Manual for dose preparation instructions.

